## Secondary Outcomes

2. Far-transfer subjective ADHD symptoms: BPT and CET will both show significant reductions in ADHD symptoms measured by unblinded parent ratings. Two scales are used: the norm-referenced BASC-2 (T-scores based on age and gender norms) and CSI-IV (raw symptom severity scores). Both have separate Attention Problems and Hyperactivity/Impulsivity subscales. Both will be tested via 2 group x 2 subscale x 2 time point mixed-model ANOVA. Critical test is the group x time interaction for both. Post-hoc plan follows #1 above.
3. Far-transfer objective (proximal) ADHD symptoms: CET will show greater reductions in actigraph-measured hyperactivity than BPT during the Rapport PH and VS working memory tests. Same 2 group x 2 task (PH-actigraphy, VS-actigraphy) x 2 time points approach as above; same post-hoc plan. Critical test is the group x time interaction. Actigraph data will be PIM intensity scores, summed across 3 actigraphs (non-dominant wrist, left ankle, right ankle).
4. Far-transfer objective (distal) ADHD symptoms: CET will show greater reductions in actigraph-measured hyperactivity than BPT during the low cognitive load Painting tasks at the beginning and end of each testing session. Same 2 group x 2 task (PaintBeginning-actigraphy, PaintEnd-actigraphy) x 2 time points approach as above; same post-hoc plan. Critical test is the group x time interaction. Actigraph data will be PIM intensity scores, summed across 3 actigraphs (non-dominant wrist, left ankle, right ankle).
5. Far-transfer subjective oppositional-defiant symptoms: BPT will show greater improvements in unblinded parent reports of oppositional defiant symptoms on the CSI-IV. Only the ADHD and ODD sections of the CSI-IV were administered. Analysis will be 2 group x 2 timepoints mixed-model ANOVA. Critical test is the group x time interaction. CSI-IV raw symptom scores for the ODD dimension will be used as dependent variable. Bonferroni-corrected paired-sample t-tests for each group separately (pre vs. post), and between-group at post covaried for pre-treatment ODD symptoms are tested because of compelling evidence that BPT improves these symptoms (manipulation check; if no significant reductions in BPT group, may indicate limited BPT efficacy).
6. Client Satisfaction Questionnaire-8 (CSQ-8) parent report at post-treatment (total scores) will be compared across groups (BPT vs. CET). No significant differences expected.

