#### Inclusion/Exclusion Criteria

All children and caregivers completed an identical evaluation, regardless of group assignment, that included detailed, semi-structured clinical interviewing (K-SADS; Kaufman et al., 1997). The K-SADS (2013 Update) assesses developmental history as well as onset, course, and impairment of DSM-5 (APA, 2013) disorders in children and adolescents. Parent and teacher ADHD ratings were obtained from the Behavior Assessment System for Children (BASC-2; Reynolds & Kamphaus, 2004) and Child Symptom Inventory (CSI-IV; Gadow & Sprafkin, 2002).

Study eligibility required all of the following (1) DSM-5 diagnosis of ADHD (any presentation) by the directing clinical psychologist based on K-SADS; (2) Borderline/clinical elevations on at least one parent and one teacher ADHD rating scale. A previous diagnosis of ADHD was also sufficient for inclusion. All children had current impairment (K-SADS). Comorbidities reflect clinical consensus best estimates. Positive screens for learning disabilities will be based on score(s) 1 SD or more below age-norms on one or more Kaufman (KTEA-2/3; 2004, 2014) academic skills battery subtests.

Medication rates will be reported. Psychostimulants were withheld for at least 24-hours prior to all research testing sessions (i.e., all working memory performance and actigraph hyperactivity data was collected off-medication).

Following convention in our assessment clinic, children prescribed psychostimulants received their usual dose during the baseline psychoeducational assessment (IQ, achievement testing) to provide the best estimates of their child's skills/abilities in the psychoeducational report provided to parents. Changes in medication status during treatment will be reported.

Children were excluded for gross neurological, sensory, or motor impairment; seizure disorder, psychosis, or intellectual disability; or non-stimulant medications that could not be withheld for testing. No inclusion/exclusion based on working memory/executive functioning performance was set.

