#### Primary Outcome

1. Near-transfer: 2 group x 2 task x 2 time points (pre, post). Tasks are Rapport phonological (PH) and visuospatial (VS) working memory tests. Critical test is the group x time interaction. The 2 tasks are included in the omnibus ANOVA to (1) address recommendations to probe cognitive abilities using multiple tests, and (2) maximize power for the critical group x time interaction. The 2 working memory tests are considered to tap the same 'central executive' working memory; they differ in whether that central executive is processing phonological or visuospatial information. If the group x time interaction is significant at  $p = .05$  (or lower), it will be followed by Bonferroni-corrected within-group post-hocs for each task and ANCOVA of post-treatment covaried for pre-treatment separately for each task (i.e., residualized gain scores). These post-hocs will also be performed if the main effect of time is significant (but not the group x time interaction) to allow us to better characterize change within each group (i.e., did each treatment produce significant change?). Stimuli correct per trial will be used.

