#### Secondary Outcomes

2. Far-transfer subjective ADHD symptoms: Two scales are used: the norm-referenced BASC-2 (T-scores based on age and gender norms) and CSI-IV (raw symptom severity scores). Both have separate Attention Problems and Hyperactivity/Impulsivity subscales. Both will be tested via 2 group x 2 subscale x 2 time point mixed-model ANOVA. Critical test is the group x time interaction for both. Post-hoc plan follows #1 above.

3. Far-transfer objective (proximal) ADHD symptoms: Same 2 group x 2 task (PH-actigraphy, VS-actigraphy) x 2 time points approach as above; same post-hoc plan. Critical test is the group x time interaction. Actigraph data will be PIM intensity scores collected while the child was completing the PH and VS tests described above. Each data point reflects total hyperactivity score (Rapport et al., 2009), which is computed by summing the PIM activity counts for each of the 3 actigraphs (non-dominant wrist, left ankle, right ankle).

4. Far-transfer objective (distal) ADHD symptoms: Same 2 group x 2 task (PaintBeginning-actigraphy, PaintEnd-actigraphy) x 2 time points approach as above; same post-hoc plan. Critical test is the group x time interaction. Actigraph data will be PIM intensity scores collected while the child was completing the beginning of session and end of session Paint activity (drawing using Microsoft Paint). Each data point reflects total hyperactivity score (Rapport et al., 2009), which is computed by summing the PIM activity counts for each of the 3 actigraphs (non-dominant wrist, left ankle, right ankle).

5. Far-transfer subjective oppositional-defiant symptoms: Included as fidelity check based on evidence that BPT may produce greatest effects on oppositional defiant symptoms. Analysis will be 2 group x 2 timepoints mixed-model ANOVA (only one measure of ODD symptoms was collected). Critical test is the group x time interaction. CSI-IV raw symptom scores for the ODD dimension will be used as dependent variable. Bonferroni-corrected paired-sample t-tests for each group separately (pre vs. post), and between-group at post covaried for pre-treatment ODD symptoms are tested because of compelling evidence that BPT improves these symptoms (manipulation check; if no significant reductions in BPT group, may indicate limited BPT efficacy).

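### Within-arm pre-post change is read as what each treatment produced, although no untreated group is followed and a shared non-specific change could be significant on its own

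*Combined protocol and SAP*

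**What the plan says.** For working memory, the Primary Outcome entry (under both Hypotheses and Statistical models) states: "Critical test is the group x time interaction". Within-group Bonferroni-corrected post-hocs follow a significant interaction. They are also run when time is significant and the interaction is not, and their purpose is put as a question: "did each treatment produce significant change".

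The Secondary Outcomes section carries this to the parent-rated ADHD scales ("Post-hoc plan follows #1 above") and to actigraphy. Hypothesis 2 reads: "BPT and CET will both show significant reductions in ADHD symptoms measured by unblinded parent ratings". The test named for it is again between arms: "Critical test is the group x time interaction for both". For oppositional-defiant (ODD) symptoms, a pre-post test within BPT serves as a manipulation check: "if no significant reductions in BPT group, may indicate limited BPT efficacy".

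Under Inclusion/Exclusion Criteria, entry called for an ADHD diagnosis and "Borderline/clinical elevations on at least one parent and one teacher ADHD rating scale", using the BASC-2 and CSI-IV. The next sentence makes a previous ADHD diagnosis sufficient as well. The parent versions of both scales are outcomes. Study design and Randomization describe two sequential, non-randomized cohorts, and Blinding says there is none. Families who did not take up treatment appear only in a pre-treatment descriptive comparison. Recommended elements takes a null result on the residualized-gain comparison as showing that the interventions are equivalent.

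**The concern.** A pre-post test has zero change as its null. It cannot separate a treatment effect from change that would have occurred anyway, so it does not support the word *produce*. For most outcomes the interaction carries the inference and the within-arm tests are secondary. Hypothesis 2 is different: an interaction says whether the arms changed by different amounts, not whether both improved, so the within-arm tests are the only evidence for it.

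Several sources of shared change are plausible: regression to the mean for children admitted on elevated ratings, expectancy in unblinded parents, elapsed time, and practice on the working memory tests. Bonferroni correction does not guard against any of them. Combined with the equivalence rule, parallel falls and no interaction would read as two equally effective treatments. Two ineffective treatments would give the same pattern.

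**Working it through.** The plan gives no power or error rate for these tests, so there is no figure to reproduce.

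**Inputs from the documents.** Expected n = 27 per arm (Sample size). Threshold .05, with Bonferroni for post-hocs (Inference criteria). Working memory retest reliability .76 to .90 (Primary Outcomes under Measures).

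**Assumptions.** Two-sided tests, counting only rejections in the improved direction. The Bonferroni family size is not stated, so .05 and .0125 (four tests) are shown. For parent ratings: scale SD 10, source mean T of 50, 60 or 65, retest reliability r of .6 to .9.

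**1. Reference.** With no change at all, a paired t-test (26 df) shows a significant improvement with probability 2.5% at .05 and 0.6% at .0125.

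**2. Regression to the mean, observed baseline fixed at mean 70, SD 8.** Expected fall = (1 − r)(70 − μ). SD of change = √[(1 − r)² × 64 + 100(1 − r²)]. For r = .8 and μ = 50, the fall is 0.2 × 20 = 4.0, the SD is √(2.56 + 36) = 6.21, and dz = 4.0/6.21 = 0.64. The noncentral t then gives 90% at .05 and 74% at .0125.

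| r | Source mean | Fall (T points) | P at .05 | P at .0125 |
|---|---|---|---|---|
| .7 | 50 | 6.0 | 98% | 92% |
| .8 | 50 | 4.0 | 90% | 74% |
| .8 | 60 | 2.0 | 36% | 18% |
| .8 | 65 | 1.0 | 12% | 4% |
| .9 | 50 | 2.0 | 62% | 39% |
| .9 | 60 | 1.0 | 20% | 8% |

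**3. Are those baselines coherent?** With an assumed cut of T ≥ 60, a source mean of 65 gives selected children a mean of 70.1 and SD of 7.0, close to the baseline in step 2. A source mean of 50 would need a cut near 66 to reach 70, with an SD of only about 3.8. The row that best fits the assumed baseline is therefore the mild one. Simulating selection directly at T ≥ 60, every child selected:

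| Source mean | Fall, r = .9 to .6 | P at .05 | P at .0125 |
|---|---|---|---|
| 50 | 1.5 to 6.1 | 41% to 96% | 21% to 87% |
| 60 | 0.8 to 3.2 | 14% to 48% | 5% to 26% |
| 65 | 0.5 to 2.0 | 8% to 22% | 3% to 9% |

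**4. Entry by previous diagnosis.** If half of the children below the cut also enter, the rate at .05 falls to about 4% to 9% across the same grid.

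**5. Working memory.** No selection was made on it, so the threat is practice or maturation. With dz = shift/√[2(1 − r)], an assumed gain of 0.2 SD gives dz = 0.29 at r = .76 and 0.45 at r = .90. The chance of a significant gain is 30% and 61% at .05, or 14% and 38% at .0125.

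**6. Same drift in both arms.** With dz = 0.5 in each arm and no treatment effect (40,000 simulated trials), the interaction is significant in 4.8% and the time effect in 95%. At .0125, at least one arm is declared changed in 73%, and both arms in 0.478² = 23%.

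**The case against.** The strongest reply is that the plan makes the interaction the critical test and describes the within-arm tests as characterizing change. For working memory and actigraphy the hypotheses are between-group, so the defect there is confined to how the follow-ups are worded. That stands. It does not rescue Hypothesis 2, which is a within-arm claim.

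A reader might infer that every child was selected on high ratings. The documents do not support this: a previous diagnosis was also sufficient, and the share entering that way is not given. Nor was there selection on working memory or ODD scores, so regression to the mean does not act directly on working memory and is at most indirect for ODD.

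A reader might also take 90% as the error rate. That figure needs a source mean of 50, pairs it with a baseline that does not fit, and ignores entry by previous diagnosis.

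For ODD, the plan says only that the absence of a fall may indicate limited efficacy. It does not say that a fall proves efficacy, though it does not rule that reading out.

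The plan also declares the parent ratings unblinded, uses age-normed BASC-2 T-scores (which removes part of maturation), and treats a barriers subscale as evidence of expectancies. These help interpretation, but none supplies the change expected without treatment.

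**Conclusion.** The concern holds as a matter of inference. Within-arm tests against zero cannot show what either treatment produced, and Hypothesis 2 depends on them. For parent ratings at n = 27 and zero effect, the chance of a significant fall at .05 from regression to the mean alone runs from under 10% to above 90%. The low end is a source mean of 65 with r = .9, or many entries by previous diagnosis. The high end is a source mean of 50 with r = .7 at a baseline of 70, or r = .6 with a cut at 60. At r = .8 and source mean 50, the two models give 90% and 71%. Nominal is 2.5% in that direction. Source mean, cut-off, rating reliability and entry route are all assumptions, so no single rate should be quoted. Expectancy and elapsed time would add to these falls.

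The documents do not support saying that the trial will declare an ineffective treatment effective. They do support saying that nothing in the plan prevents it for the parent-rated outcomes.

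**What to change.** - **Primary Outcome (Hypotheses and Statistical models) and Secondary Outcomes (Statistical models):** replace the question "did each treatment produce significant change", and its carry-over, with whether scores changed within each group. Report these results as descriptive mean change with a confidence interval.
- **Hypothesis 2:** reword as a prediction of pre-post change, not of a treatment effect.
- **Inference criteria:** state that efficacy relative to BPT is concluded only from the between-arm contrast with its confidence interval, with the non-randomized design named as a limit.
- **Recommended elements (both places):** remove the equivalence reading. State that parallel falls without an interaction show neither that either treatment works nor that the two are equivalent.
- **ODD check:** state that a significant fall in BPT does not by itself confirm BPT efficacy.

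An expected regression-to-the-mean value should not replace zero as a test threshold. It needs the source mean as well as the baseline mean and reliability, and at r = .8 and baseline 70 that one unknown moves the fall from 4 to 1 T points. At most, show it as a sensitivity range over stated source means and reliabilities.

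The cost is wording only, with no new data. The real price is weaker within-group claims, including the part of research question 3 that asks whether CET itself improves ADHD symptoms: with an active comparator and no untreated group, this design gives only limited evidence on that.

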#### Secondary Outcomes

2. Far-transfer subjective ADHD symptoms: Two scales are used: the norm-referenced BASC-2 (T-scores based on age and gender norms) and CSI-IV (raw symptom severity scores). Both have separate Attention Problems and Hyperactivity/Impulsivity subscales. Both will be tested via 2 group x 2 subscale x 2 time point mixed-model ANOVA. Critical test is the group x time interaction for both. Post-hoc plan follows #1 above.

3. Far-transfer objective (proximal) ADHD symptoms: Same 2 group x 2 task (PH-actigraphy, VS-actigraphy) x 2 time points approach as above; same post-hoc plan. Critical test is the group x time interaction. Actigraph data will be PIM intensity scores collected while the child was completing the PH and VS tests described above. Each data point reflects total hyperactivity score (Rapport et al., 2009), which is computed by summing the PIM activity counts for each of the 3 actigraphs (non-dominant wrist, left ankle, right ankle).

4. Far-transfer objective (distal) ADHD symptoms: Same 2 group x 2 task (PaintBeginning-actigraphy, PaintEnd-actigraphy) x 2 time points approach as above; same post-hoc plan. Critical test is the group x time interaction. Actigraph data will be PIM intensity scores collected while the child was completing the beginning of session and end of session Paint activity (drawing using Microsoft Paint). Each data point reflects total hyperactivity score (Rapport et al., 2009), which is computed by summing the PIM activity counts for each of the 3 actigraphs (non-dominant wrist, left ankle, right ankle).

5. Far-transfer subjective oppositional-defiant symptoms: Included as fidelity check based on evidence that BPT may produce greatest effects on oppositional defiant symptoms. Analysis will be 2 group x 2 timepoints mixed-model ANOVA (only one measure of ODD symptoms was collected). Critical test is the group x time interaction. CSI-IV raw symptom scores for the ODD dimension will be used as dependent variable. Bonferroni-corrected paired-sample t-tests for each group separately (pre vs. post), and between-group at post covaried for pre-treatment ODD symptoms are tested because of compelling evidence that BPT improves these symptoms (manipulation check; if no significant reductions in BPT group, may indicate limited BPT efficacy).

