### Variables

*Please list each research question included in this study.*

1. Is CET a feasible and acceptable intervention for caregivers and their children with ADHD? Is its feasibility and acceptability comparable to the current gold-standard psychosocial treatment for ADHD (BPT)?
2. Does CET improve working memory in children with ADHD, and are these improvements superior to those found for BPT (which is not expected to improve working memory)?
3. Does CET improve ADHD symptoms in children with ADHD, and are these improvements non-inferior to improvements associated with gold-standard BPT?
4. (Fidelity Check) Does BPT improve oppositional-defiant symptoms in children with ADHD, and how does CET compare to BPT for these expected improvements?

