#### Treatments

##### Behavioral Parent Training (BPT)

Evidence-based behavioral parent training (BPT; Evans et al., 2014) was provided using the Barkley (2013) Defiant Child protocol. BPT was delivered with fidelity in small group format by behaviorally trained, PhD-level clinicians ([name], [name], [name]).

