#### Recommended elements

10. All hypothesized interactions are expected to look like Figure 1 in Redick (2015). In other words, no pre-treatment group differences, and differential improvements favoring the group hypothesized to improve. Should pre-treatment group differences be observed, differential improvements favoring the group hypothesized to improve would be observed when using post-treatment covaried for pre-treatment analysis (residualized gain scores). No differences in this test indicate equivalence between interventions.

11. P-values and Bayes Factors will be reported. P-values will be considered primary in cases of discrepant results (to follow current conventions in the field). P-values = .05 or lower will be considered significant (after Bonferroni corrections for post-hoc tests). Bayes Factors = 3 or greater will be considered significant.

no file selected

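### No rule stops an equivalence conclusion for CET against BPT on ADHD symptoms when BPT itself shows no ADHD improvement

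*Combined protocol and SAP*

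**What the plan says.** Research question 3 is framed against the comparator's effect on ADHD symptoms: "Does CET improve ADHD symptoms in children with ADHD, and are these improvements non-inferior to improvements associated with gold-standard BPT".

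Hypothesis 2 (Hypotheses, Secondary Outcomes, item 2) predicts that "BPT and CET will both show significant reductions in ADHD symptoms measured by unblinded parent ratings".

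For the analysis of those ratings, the Analysis Plan (Secondary Outcomes, item 2) says: "Critical test is the group x time interaction for both. Post-hoc plan follows #1 above". Item 1 sets the post-hoc plan. If group x time is significant, "it will be followed by Bonferroni-corrected within-group post-hocs for each task and ANCOVA of post-treatment covaried for pre-treatment separately for each task". It adds a second trigger: "These post-hocs will also be performed if the main effect of time is significant (but not the group x time interaction".

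Item 5 treats oppositional symptoms differently. Pre-post tests in each group are planned with no omnibus condition. The stated reason is: "Included as fidelity check based on evidence that BPT may produce greatest effects on oppositional defiant symptoms". The plan adds that the absence of a significant reduction in the BPT group may point to limited BPT efficacy.

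Recommended elements (item 1 in the Hypotheses, item 10 in the Analysis Plan) says of the post-treatment comparison covaried for pre-treatment: "No differences in this test indicate equivalence between interventions".

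**The concern.** Matching an active comparator is informative only if the comparator worked, in this study, on the outcome being compared. If BPT as delivered did nothing for parent-rated ADHD symptoms, a CET arm that looks no different from it has not been shown to match an effective treatment. That holds with or without a non-inferiority margin, so this is a separate matter from the missing margin.

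The plan sees the need for such a check, but attaches it unconditionally only to oppositional symptoms, where it expects BPT may do most. For ADHD symptoms it has a prediction and a conditional test. Nothing says what follows for research question 3 if BPT fails that test. At stake is a published statement that CET is equivalent to a gold-standard treatment on ADHD symptoms, from data in which that treatment showed no ADHD benefit.

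**Working it through.** **The rules for the two outcomes, side by side**

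- *Within-BPT pre-post test.* Oppositional symptoms: always run. ADHD ratings: run only if group x time or the pooled time effect is significant.
- *Stated meaning of a BPT failure.* Oppositional symptoms: possible limited efficacy. ADHD ratings: none, beyond contradicting hypothesis 2.
- *Link to the equivalence sentence.* None for either outcome.

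**How often the problem path arises**

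The plan gives no power, effect size, SD or margin, so there is no figure to reproduce. The path of interest has three parts: group x time is null, the pooled time effect is significant (so the post-hocs run), and BPT shows no significant ADHD improvement.

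Inputs from the documents: 27 per arm (Sample size); significance at 0.05 with no correction of omnibus tests (Inference criteria); two subscales per model.

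Assumptions: two-sided tests; each subscale change has SD 1; correlation 0.5 between the two subscale changes; true BPT change zero; Bonferroni over 2 groups x 2 subscales, so 0.05/4 = 0.0125; one rating scale at a time.

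Average each child's change over the two subscales. The SD of that average is sqrt((1 + 0.5)/2) = 0.866. With arm means mB and mC and pooled SD s, both tests have 52 df:

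- group x time: t = (mC − mB) / (s·sqrt(2/27))
- pooled time: t = ((mB + mC)/2) / (s·sqrt(1/54))

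When BPT's true change is zero, both tests have the same noncentrality, d·sqrt(27/2) = 3.674·d, where d is CET's change in SDs of the averaged score. CET's own change is therefore as likely to make pooled time significant as to make group x time significant. The two can easily disagree.

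Simulation (20,000 trials per row, BPT true change zero, d in SDs of the averaged change):

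| CET d | Group x time null | Pooled time significant | Both | Both, and BPT not significant on either subscale |
|---|---|---|---|---|
| 0 | 95.2% | 5.1% | 4.9% | 4.5% |
| 0.2 | 89.1% | 11.1% | 9.8% | 9.0% |
| 0.3 | 80.9% | 19.3% | 15.1% | 14.1% |
| 0.5 | 56.7% | 43.6% | 24.1% | 23.1% |
| 0.8 | 17.9% | 82.0% | 14.2% | 13.3% |

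Expressed in SDs of a single subscale's change, 0.3 is d = 0.3/0.866 = 0.346 and 0.5 is d = 0.5/0.866 = 0.577. The last column is then about 17% and 23%.

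The simulation counts a null group x time test. It does not model the baseline-adjusted ANCOVA, which would need a pre-post correlation that the plan does not give. The figures show how often the situation arises, not how often equivalence would be declared.

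**What the proposed condition can detect**

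Paired t-test, 27 children, 26 df, two-sided 0.05, noncentrality dz·sqrt(27) = 5.196·dz. At dz = 0.5 this is 2.60 and power is 71%. Power is 32% at dz = 0.3 and 98% at dz = 0.8, and reaches 80% at dz = 0.56. If BPT's true change is zero, a 95% CI excludes zero in the improving direction 2.5% of the time on a given subscale.

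**The case against.** The strongest reply is that the equivalence test and the within-BPT test open together. The equivalence sentence refers to the covaried post-treatment comparison. For ADHD ratings that ANCOVA is itself a post-hoc, under the same triggers as the within-group tests. On the natural reading, whenever equivalence could be declared, BPT's ADHD change has also been tested and would be reported. This stands. A reader might infer that BPT could fail on ADHD symptoms untested and still be the benchmark; the documents do not generally support that. One caveat: Recommended elements brings in the covaried analysis for the case of baseline differences, and could be read as allowing it outside those triggers.

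A reader might also infer that a pass on oppositional symptoms certifies BPT for the ADHD comparison. The plan never says so. The check is stated only in the negative direction and belongs to research question 4. Nor does a greatest effect on oppositional symptoms imply no effect on ADHD symptoms.

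For the same reason it would mislead to count every trial with a null group x time test and a passed oppositional check. With an assumed BPT oppositional change of 0.6 SD, independent of ADHD change and tested at 0.025, that count is 73% when neither arm changes ADHD symptoms and 58% when CET changes by 0.3 SD. But about 69 of the 73 points and 45 of the 58 have no trigger met, so no equivalence ANCOVA is run. Pooled time is then not significant either, which leaves the first half of research question 3, whether CET improves ADHD symptoms, unsupported.

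Hypothesis 2 is also a registered prediction that an inert BPT arm would contradict. That is fair, but a failed prediction with no stated consequence does not restrain the equivalence sentence.

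Finally, a pre-post condition is imperfect. Any numerical fall would pass about half the time under no change, and regression to the mean could satisfy even a significance rule. Both points shape the fix; neither removes the gap.

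**Conclusion.** The concern holds in a limited form. The main gap is not an untested BPT arm but a missing rule: the plan reads no difference as equivalence and does not say that BPT's failure to improve ADHD symptoms blocks that reading.

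The situation in which this matters arises in about 17% of trials if CET changes by 0.3 SD and 23% at 0.5 SD. These figures rest on 27 per arm, a BPT arm truly inert on ADHD symptoms, a subscale-change correlation of 0.5 and post-hocs at 0.0125. Only the sample size comes from the plan. The plan also tests two rating scales, whereas the calculation treats one. The point affects the interpretation of a secondary outcome and leaves the primary working memory test untouched.

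**What to change.** 1. In item 2 of Secondary Outcomes, in both the Hypotheses and the Analysis Plan, state that the within-BPT pre-post change with its 95% CI will always be reported for the parent-rated ADHD subscales of the BASC-2 and the CSI-IV, whatever the omnibus result.
2. In Recommended elements (item 1 in the Hypotheses, item 10 in the Analysis Plan), add: a comparable or non-inferior result on ADHD symptoms is claimed only if the 95% CI for BPT's pre-post change on that same outcome excludes zero in the direction of improvement; otherwise the comparison with BPT in research question 3 is reported as inconclusive.
3. State that this is a necessary condition only. It does not replace a margin, and a pre-post fall in unblinded ratings can reflect regression to the mean.
4. Keep the oppositional-symptom check under research question 4 and do not use it to support research question 3.

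The cost is a few sentences and one extra contrast per ADHD subscale on data already planned. The downside is that, at about 71% power for a standardised change of 0.5, the claim will sometimes be withheld although BPT worked.
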